11.6 Study Design

This study is designed using a rolling six model to confirm the recommended phase 2 dose or maximally tolerated dose of Palbociclib in patients with relapsed B- or T-ALL/LL. Once the RP2D/MTD is established a non-statistical feasibility expansion cohort of up to 6 evaluable patients will be enrolled. If the proportion of patients who experience a DLT in cycle 1 is >33% at any time, then the study will suspend enrollment pending DVL leadership discussion.

11.7 Method of Analysis

Response will be determined as defined in Section 12.0. A report on the efficacy assessment will be posted on the completed disease stratum as part of a semi-annual study committee meeting book report.

Toxicities for patients will be described separately for the expansion cohort.

12.0 EVALUATION CRITERIA

12.1 Common Terminology Criteria for Adverse Events (CTCAE)

The descriptions and grading scales found in the revised NCI Common Terminology Criteria for Adverse Events (CTCAE) version 5.0 will be utilized for AE reporting. All appropriate treatment areas should have access to a copy of the CTCAE version 5.0. A copy of the CTCAE version 5.0 can be downloaded from the CTEP website (<http://ctep.cancer.gov>).

12.2 Response Criteria for Patients with Relapsed Acute Lymphoblastic Leukemia

12.2.1 Bone marrow status

M1 < 5% blasts in a bone marrow aspirate with at least 200 cells counted.

M2 5 - 25% lymphoblasts in a bone marrow aspirate with at least 200 cells counted.

M3 > 25% lymphoblasts in a bone marrow aspirate with at least 200 cells counted.

12.2.2 Leukemia Relapse

- **Isolated Bone Marrow Relapse:** Patients with an M2 or M3 marrow at any point after achieving initial remission without involvement of any extramedullary site. Morphologic relapse should be confirmed using flow cytometry, FISH and/or cytogenetics or molecular techniques.
- **CNS Relapse:** Positive cytomorphology and WBC $\geq 5/\mu\text{L}$ OR clinical signs of CNS leukemia such as facial nerve palsy, brain/eye involvement, or hypothalamic syndrome that are, in the opinion of the investigator, more likely due to recurrent CNS leukemia than to alternative causes (e.g., viral infection or chemotherapy toxicity). If any CSF evaluation shows positive cytomorphology and WBC $< 5/\mu\text{L}$, a second CSF evaluation is recommended within 2 - 4 weeks. While identification of a leukemic clone in CSF by flow cytometry (TdT, CD19, CD10, etc.) or FISH for diagnostic karyotypic abnormality may be useful, definitive evidence of CNS

involvement (i.e. $WBC \geq 5/\mu L$ OR clinical signs of CNS leukemia) is required for the diagnosis of a CNS relapse.

- **Testicular Relapse:** Confirmation by testicular biopsy preferred but not required if associated with marrow relapse.
- **Combined Relapse:** M2 or M3 marrow at any point after achieving remission with concomitant CNS and/or testicular relapse.

12.2.3 Complete Response (CR)

Complete response (CR) is defined as an M1 marrow (< 5% blasts) with no evidence of circulating blasts or extramedullary disease and with peripheral count recovery, defined as absolute neutrophil count (ANC) $\geq 500/\mu L$ and platelet count \geq to 50,000/ μL without transfusion for 7 days.

Resolution of extramedullary disease (non-CNS, non-testicular) is defined as improvement of any nodal or organ disease with lesion resolution to < 1cm or FDG-PET SUV improved to Deauville 3 or less (< hepatic or mediastinal uptake) if initially FDG-avid. Skin lesions must be clinically resolved.

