12.2.4 Complete Response with Incomplete Count Recovery (CRi)

Complete response with incomplete recovery of peripheral blood counts (CRi) is defined as an M1 marrow (< 5% blasts) with no evidence of circulating blasts or extramedullary disease and with an ANC < 500/ μL and/or platelet count < 50,000/ μL .

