12.2.5 Partial Response (PR)

Complete disappearance of circulating blasts and achievement of M2 marrow status if M3 originally, without new sites of extramedullary disease, and with recovery of absolute neutrophil count (ANC $\geq 500/\mu L$). Complete response in the marrow without resolution of extramedullary sites is a PR.

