12.2.6 Stable Disease (SD)

Patient does not satisfy the criteria for PD, or has recovery of ANC $\geq 500/\mu L$ and fails to qualify for CR, CRi, or PR.

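### Read literally, the ALL response categories place a patient in marrow remission with ANC ≥ 500/µL and platelets ≥ 50,000/µL, but transfused within 7 days, in stable disease rather than CR or CRi

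*Combined protocol and SAP*

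**What the plan says.** The ALL response categories are in section 12.2 of the combined protocol and SAP.

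- **CR (12.2.3).** The disease part reads "Complete response (CR) is defined as an M1 marrow (< 5% blasts) with no evidence of circulating blasts or extramedullary disease". Count recovery is then defined as ANC ≥ 500/µL and platelets ≥ 50,000/µL "without transfusion for 7 days". The type of transfusion is not stated.
- **CRi (12.2.4).** "Complete response with incomplete recovery of peripheral blood counts (CRi) is defined as an M1 marrow", with the same disease state as CR. The count conditions are "extramedullary disease and with an ANC < 500"/µL "and/or platelet count < 50,000"/µL. Transfusion is not mentioned.
- **PR (12.2.5).** There are two routes: "achievement of M2 marrow status if M3 originally", or residual disease outside the marrow ("Complete response in the marrow without resolution of extramedullary sites is a PR").
- **SD (12.2.6).** This takes the patient whose ANC has recovered to 500/µL and who "fails to qualify for CR, CRi, or PR".
- **Treatment failure (12.2.9).** Failure is avoided by M1 marrow, CNS1 and resolution of extramedullary disease. Neither counts nor transfusion enter.

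Response serves a secondary aim (1.2.1) and is to be reported descriptively (11.5).

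**The concern.** CR and CRi should between them cover every patient in marrow remission with no disease elsewhere: CR if the counts have recovered, CRi if they have not. They do so only if CRi is the complement of CR's count-recovery condition. Here CR's condition has three parts (ANC, platelets, freedom from transfusion) and CRi negates only two of them. A patient who fails CR solely on the transfusion clause has no response category to go to.

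At stake is the activity summary for ALL. A marrow remission, possibly one that is MRD-negative under 12.2.8, would be listed as SD. The error can run in only one direction, from response to non-response. Sites that follow the intent of CRi and sites that follow its wording would also code identical patients differently.

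**Working it through.** The plan gives no figure to reproduce on this point, so the check is to apply the rules to every possible state.

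**Inputs.** The CR, CRi, PR and SD definitions in 12.2.3 to 12.2.6, with M1 (< 5% blasts) and M2 (5–25% blasts) from 12.2.1.

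**States.** Fix the patient at M1 marrow, no blood blasts, no extramedullary disease and no progression. Four items vary: baseline marrow (M2 or M3), ANC (≥ or < 500/µL), platelets (≥ or < 50,000/µL) and transfusion within 7 days (yes or no). That gives 2 × 2 × 2 × 2 = 16 states. The result is the same for both baseline marrows, so the table shows 8 rows.

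| ANC (/µL) | Platelets (/µL) | Transfused within 7 days | Category as written |
|---|---|---|---|
| ≥ 500 | ≥ 50,000 | no | CR |
| ≥ 500 | ≥ 50,000 | **yes** | **SD** |
| ≥ 500 | < 50,000 | no | CRi |
| ≥ 500 | < 50,000 | yes | CRi |
| < 500 | ≥ 50,000 | no | CRi |
| < 500 | ≥ 50,000 | yes | CRi |
| < 500 | < 50,000 | no | CRi |
| < 500 | < 50,000 | yes | CRi |

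Over both baselines: 2 states are CR, 12 are CRi and 2 are SD (2 + 12 + 2 = 16).

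**The SD row, step by step.**
1. CR fails because of the transfusion.
2. CRi fails because ANC is not below 500/µL and platelets are not below 50,000/µL.
3. PR fails by the marrow route because M1 is not M2, and by the other route because no extramedullary disease remains.
4. Under 12.2.6, ANC is recovered and CR, CRi and PR are all missed, so the category is SD.

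**Ordering.** Take a transfused patient with ANC ≥ 500/µL. At 49,000/µL platelets the category is CRi; at 50,000/µL it is SD. Or take a transfused patient with platelets ≥ 50,000/µL: with ANC < 500/µL the category is CRi, and with ANC ≥ 500/µL it is SD. Either way, the better count gives the worse category.

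**Against 12.2.9.** The same patient, if CNS1, has met every condition for avoiding treatment failure, yet is recorded as SD.

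**Weight of one case.** The change in a CR+CRi proportion is 1/n: 1/6 = 16.7 points, 1/12 = 8.3 points, 1/21 = 4.8 points. These values of n are illustrative. The plan states no response denominator, and lymphoma patients are assessed under 12.4 rather than 12.2.

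**The case against.** The best defence is purposive. Section 12.2.3 defines count recovery as one package, and 12.2.4 is titled for incomplete count recovery, so a patient who misses only the transfusion part plainly belongs in CRi. Section 12.2.6 itself cannot be read to the letter: its opening alternative would make every patient without progression SD, including a clear CR. If that section must be read for its purpose, so may 12.2.4. This is fair, and many investigators would code CRi. But the operative text of 12.2.4 is numeric and complete in itself, and nothing elsewhere says how to class a transfused count of 50,000/µL or more. A lenient reading of PR as M2 or better would rescue only patients who started at M3; a patient who started at M2 would still be SD.

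A second defence is follow-up. Section 8.1 requires repeat marrows at Day 42 and beyond when count recovery is delayed, so the patient may qualify as CR later. This mitigates the problem in part. The text does not say whether a transfused count is delayed recovery, nor which assessment sets the reported response.

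Three stronger readings might be inferred, and the documents support none of them:

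- **Every recently transfused patient in remission loses response status.** No: with ANC < 500/µL or platelets < 50,000/µL the patient is CRi.
- **Transfusion is routine here, so the bias is material.** Section 7.3 says only that blood products are given as needed. No rate, threshold or Day 32 platelet distribution is stated.
- **The response estimate is biased by 5 to 17 points.** Those figures are the weight of one case, not an expected bias. The plan does not define a CR+CRi rate as an endpoint.

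**Conclusion.** The gap holds on the text. One combination of counts and transfusion, reached from either baseline marrow (2 of 16 states), falls out of CR and CRi and into SD, and the categories are misordered at both count thresholds. This is a stated rule that gives a wrong category, not merely missing detail.

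The size is limited. The frequency is unknown; each case would move a descriptive CR+CRi proportion by 1/n. Only ALL patients are affected, and only in a secondary, exploratory summary. The DLT definition, the MTD rule, dose decisions and sample size do not depend on it. MRD status and treatment failure are defined separately, so the remission would still be visible in patient-level data.

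The conclusion assumes that the CRi thresholds apply to the measured counts, as 12.2.4 states them, and that 12.2.6 works as the residual category. If the unspecified transfusion in 12.2.3 also covers red cells, the gap is wider.

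**What to change.** In 12.2.4, define CRi as M1 marrow with no blasts in the blood and no extramedullary disease, in a patient who does not meet the full count-recovery definition of 12.2.3: ANC < 500/µL, or platelets < 50,000/µL, or transfusion within 7 days. In both sections, specify that the transfusion meant is platelet transfusion.

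With this change, all 16 states above fall in exactly one of CR (2) or CRi (14), and none reaches SD.

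The cost is one sentence plus one clarifying word in 12.2.3. No new data are needed, because CR already requires the transfusion date at response assessment. The change should be made before responses are tabulated, so that all ALL patients are classed under the same rule.

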12.2.4 Complete Response with Incomplete Count Recovery (CRi)

Complete response with incomplete recovery of peripheral blood counts (CRi) is defined as an M1 marrow (< 5% blasts) with no evidence of circulating blasts or extramedullary disease and with an ANC < 500/ μL and/or platelet count < 50,000/ μL .

12.2.5 Partial Response (PR)

Complete disappearance of circulating blasts and achievement of M2 marrow status if M3 originally, without new sites of extramedullary disease, and with recovery of absolute neutrophil count (ANC $\geq 500/\mu L$). Complete response in the marrow without resolution of extramedullary sites is a PR.

12.2.6 Stable Disease (SD)

Patient does not satisfy the criteria for PD, or has recovery of ANC $\geq 500/\mu L$ and fails to qualify for CR, CRi, or PR.

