12.2.7 Progressive Disease (PD)

An increase of at least 25% in the absolute number of bone marrow leukemic cells, development of new sites of extramedullary disease, or other laboratory or clinical evidence of PD, with or without recovery of ANC or platelets.

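### The stable-disease definition for ALL also admits progressing patients whose ANC has recovered, and the protocol gives no order of precedence

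*Combined protocol and SAP*

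**What the plan says.** The ALL response categories are set out in Sections 12.2.3 to 12.2.7.

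- **SD (12.2.6):** "Patient does not satisfy the criteria for PD, or has recovery of ANC" to at least 500/µL "and fails to qualify for CR, CRi, or PR".
- **PD (12.2.7):** "An increase of at least 25% in the absolute number of bone marrow leukemic cells, development of new sites of extramedullary disease". Any further sign of progression, clinical or from the laboratory, also counts. The section adds that PD applies "with or without recovery of ANC or platelets".
- **CR (12.2.3):** "is defined as an M1 marrow (< 5% blasts) with no evidence of circulating blasts or extramedullary disease and with peripheral count recovery".
- **CRi (12.2.4):** the same marrow and disease conditions, with ANC below 500/µL and/or platelets below 50,000/µL.
- **PR (12.2.5):** two routes. One is "Complete disappearance of circulating blasts and achievement of M2 marrow status if M3 originally, without new sites of extramedullary disease", with ANC recovery. The other is "Complete response in the marrow without resolution of extramedullary sites is a PR".

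The lymphoblastic lymphoma criteria in Section 12.4.5.1 treat SD differently. There it is a true residual, requiring that the thresholds for both PR and PD are missed.

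Section 11.5 says that response will be reported descriptively using the Section 12 criteria. Section 11.7 bases the efficacy report on the same criteria, and Appendix IV correlates baseline markers with treatment response.

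**The concern.** Response categories that are tabulated as proportions should be mutually exclusive and should cover every assessed patient. In Section 12.2.6 the exclusion of PD stands before the *or*, and the exclusion of CR, CRi and PR stands after it. No single alternative carries both exclusions. A patient can enter SD through the second alternative while progressing, because that alternative asks only for ANC recovery and absence of response.

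Two sites, or one site on two occasions, could then code the same progressing patient as SD or as PD and both be following the text. The analyses of antitumor activity are descriptive, so the category counts are themselves the result. No later model or test would absorb inconsistent coding.

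**Working it through.** There is no figure in the plan to reproduce. The question is one of logic, so the definitions were coded and applied to every combination of the features they use.

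**Inputs (Sections 12.2.1 and 12.2.3 to 12.2.7).** Baseline marrow M2 or M3 (2); end-of-cycle marrow M1, M2 or M3 (3); circulating blasts yes/no (2); extramedullary disease absent or resolved, persisting, or new (3); ANC at least 500/µL yes/no (2); platelets recovered, low, or adequate only with transfusion (3); marrow rise of at least 25% yes/no (2); other evidence of PD yes/no (2).

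**Number of profiles.** 2×3×2×3×2×3×2×2 = 864, or 144 for each baseline-by-end marrow pair. Impossible combinations were removed:

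- a 25% rise with an M1 marrow: 2×72 = 144;
- a 25% rise with M3 falling to M2: 72;
- M2 rising to M3 without a 25% rise: 72.

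This leaves 864 − 288 = 576.

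**Assumptions.** CR and CRi profiles carry no other evidence of PD. A marrow CR in the second PR route includes recovery of ANC and platelets.

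**Rules for SD compared.**

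- A, literal: not PD, or (ANC recovered and not CR/CRi/PR).
- B, charitable, with the last clause governing the whole sentence: (not PD or ANC recovered) and not CR/CRi/PR.
- C, *or* replaced by *and*: not PD, ANC recovered, and not CR/CRi/PR.
- D, residual: not PD and not CR/CRi/PR, whatever the ANC.

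| Profiles that also meet SD | A | B | C | D |
|---|---|---|---|---|
| CR | 2/2 | 0/2 | 0/2 | 0/2 |
| CRi | 8/8 | 0/8 | 0/8 | 0/8 |
| PR without PD | 8/8 | 0/8 | 0/8 | 0/8 |
| PD, ANC recovered, not PR | 216/216 | 216/216 | 0/216 | 0/216 |
| PD, ANC not recovered | 0/228 | 0/228 | 0/228 | 0/228 |
| In more than one category, of 576 | 246 | 228 | 12 | 12 |
| In no category, of 576 | 0 | 0 | 54 | 0 |

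The totals reconcile: 2 + 8 + 8 + 216 + 12 = 246 under A, and 216 + 12 = 228 under B.

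**The 12 that remain under C and D** meet both PR and PD and come from Sections 12.2.5 and 12.2.7, not from the SD rule. In four, a marrow CR coexists with a new extramedullary site. The second PR route carries no condition against new sites, while a new site is PD. In the other eight, a PR coexists with other evidence of PD.

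**The 54 without a category under C** are all non-PD, non-responding profiles with ANC below 500/µL: 24 with M2 marrow, 12 with M3 and 18 with M1 and residual disease.

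These are counts of logical profiles, not expected numbers of patients.

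**The case against.** **An investigator would code sensibly.** CR, CRi and PR have their own definitions, and nobody is likely to record a complete responder as SD. If the closing clause governs the whole sentence, the responder overlap disappears (column B). This stands: a reader might infer that every responder is also SD, but that holds only on the literal reading. The punctuation favours that reading without compelling it. The objection does not remove the overlap with PD, which is the same in A and B. The remark in Section 12.2.7 that PD does not depend on count recovery hints that PD should prevail, but it is not a precedence rule.

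**The ANC condition may be deliberate.** Section 8.1, footnote 4, calls for a repeat marrow by Day 42 when counts are delayed, then every 7 to 14 days until recovery or relapse. A patient without ANC recovery might simply be classified later. This has some force. However, Section 10.2 takes patients off study 30 days after the last dose of investigational agent. With palbociclib ending on Day 21, that is Day 51 (21 + 30), so a later classification is not assured.

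**A bare residual definition has its own fault.** It would make SD the default for a patient with no end-of-cycle assessment, for example after an early death. This stands, and an assessment condition is needed. A residual rule also makes SD of a patient with M1 marrow, no other disease, recovered ANC and platelets held up only by transfusion, who meets neither CR nor CRi. The literal rule already does the same, so that gap lies in the CR and CRi definitions.

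**Little depends on it.** Response is descriptive. The DLT and MTD rules (Sections 5.4, 11.2.2 and 11.3), MRD negativity and treatment failure (Sections 12.2.8 and 12.2.9) do not refer to SD. This stands and limits the weight of the point.

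**Conclusion.** The defect is real but narrow. As written, a patient with PD, recovered ANC and no PR is also SD under either parsing, and nothing in Section 12.2 or Section 11 settles which label applies. On the literal reading, non-progressing CR, CRi and PR patients are SD as well. What is affected is the ALL response tabulation for secondary aim 1.2.1 and the exploratory correlations in Appendix IV.

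Four stronger statements might be inferred and are not supported:

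- *Every progressing patient with recovered ANC is also SD.* The 12 profiles that meet both PR and PD are not SD.
- *A residual SD rule by itself gives each patient one category.* It does not, because the PR/PD overlap remains.
- *The protocol leaves ALL response to institutional evaluation.* That sentence is in Section 12.4.8.4, within the lymphoma criteria; Section 12.2 contains no equivalent.
- *Each miscoded patient moves a rate by 8.3 percentage points.* That is 1/12, using 6 dose-confirmation plus up to 6 expansion patients, and it pools ALL with LL. The ALL denominator is not stated. For illustration only, one patient is 8.3 points if all 12 have ALL and 16.7 points (1/6) if 6 do.

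The documents give no basis for an expected number of miscoded patients.

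**What to change.** Replace Section 12.2.6 with a residual definition along these lines: *SD: an end-of-cycle disease assessment is available and shows none of CR, CRi, PR or PD, whatever the ANC.*

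Add two sentences to Section 12.2:

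- PD takes precedence over every other category, including PR. This also settles the overlap between Sections 12.2.5 and 12.2.7.
- Patients without an end-of-cycle assessment are reported as not assessed and are not counted as SD.

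Do not simply exchange *or* for *and*: non-progressing, non-responding patients with ANC below 500/µL would then have no category at that assessment.

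The cost is a few sentences of protocol text and the matching response-coding instruction. No additional patients, samples or visits are needed.

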12.2.7 Progressive Disease (PD)

An increase of at least 25% in the absolute number of bone marrow leukemic cells, development of new sites of extramedullary disease, or other laboratory or clinical evidence of PD, with or without recovery of ANC or platelets.

12.2.8 MRD Negative

Patients will be considered MRD negative if their bone marrow has less than 0.01% blasts by flow cytometric evaluation. MRD should be performed by a COG approved laboratory.

12.2.9 Treatment Failure: Failure to achieve the following:

	Marrow	CNS	Testicular/Other Extramedullary Disease
End of Cycle 1	M1	CNS1	Clinical and imaging resolution (if

			applicable) of all sites of extramedullary disease
--	--	--	--

12.3 Central Nervous System (CNS) involvement of leukemia or lymphoma at relapse

CNS 1: In cerebral spinal fluid (CSF), absence of blasts on cytopsin preparation, regardless of the number of WBCs.

CNS 2: In CSF, presence < 5/μL WBCs and cytopsin positive for blasts, or ≥ 5/μL WBCs but negative by Steinherz/Bleyer algorithm:

CNS 2a: < 10/μL red blood cells (RBCs); < 5/μL WBCs and cytopsin positive for blasts;

CNS 2b: ≥ 10/μL RBCs; < 5/μL WBCs and cytopsin positive for blasts; and

CNS 2c: ≥ 10/μL RBCs; ≥ 5/μL WBCs and cytopsin positive for blasts but negative by Steinherz/Bleyer algorithm (see below);

CNS 3: In CSF, presence of ≥ 5/μL WBCs and cytopsin positive for blasts **and/or** clinical signs of CNS leukemia or lymphoma:

CNS 3a: < 10/μL RBCs; ≥ 5/μL WBCs and cytopsin positive for blasts;

CNS 3b: ≥ 10/μL RBCs; ≥ 5/μL WBCs and positive by Steinherz/Bleyer algorithm (see below);

CNS 3c: Clinical signs of CNS leukemia or lymphoma (such as facial nerve palsy, brain/eye involvement or hypothalamic syndrome).

Method of evaluating initial traumatic lumbar punctures (LPs)

If the patient has leukemic cells in the peripheral blood and the lumbar puncture is traumatic and contains ≥5 WBC/μL and blasts, the following Steinherz/Bleyer algorithm should be used to distinguish between CNS2 and CNS3 disease:

$$\frac{\text{CSF WBC}}{\text{CSF RBC}} > 2X \frac{\text{Blood WBC}}{\text{Blood RBC}}$$

A patient with CSF WBC ≥5/μL blasts, whose CSF WBC/RBC ratio is 2X greater than the blood WBC/RBC ratio, has CNS disease at diagnosis.

Example: CSF WBC = 60/μL; CSF RBC = 1,500/μL; blood WBC = 46000/μL; blood RBC = 3.0 X 10⁶/μL:

$$\frac{60}{1,500} = 0.04 > 2X \frac{46,000}{3.0 \times 10^6} = 0.015$$

